10 STATISTICAL CONSIDERATIONS

10.1 COHORT 1

10.1.1 Primary Objective

The primary objective is to evaluate the non-inferiority of patient Health Related Quality of Life (HRQOL) in the Experimental arm compared to the Control arms one month after treatment. The primary efficacy variable is the Global Health status from the EORTC QLQ-C30. The EORTC QLQ-C30 is a multidimensional, cancer-specific quality of life questionnaire developed by the EORTC Study Group on Quality of Life (QOL) for repeated assessments within clinical trials. All patients with valid non-missing baseline and one month follow up Global Health Status will be included in the analysis. See below for handling of missing items.

The primary hypothesis is that the Global Health Status is non-inferior in the Experimental Arm compared to the Control Arm. Let μ_E and μ_C be the mean Global Health status in the Experimental and Control Arms respectively. The null hypothesis (H_0) and alternative hypothesis (H_1) are

$$H_0: \mu_E - \mu_C \leq -15 \text{ and } H_1: \mu_E - \mu_C > -15$$

A two sample t test will be used for the primary analysis. As a sensitivity analysis we will use analysis of covariance with Global Health Status at one month post therapy as Gaussian response variable, treatment group as a fixed effect and baseline Global Health Status as a continuous adjustment variable.

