8 STUDY CALENDAR

Examination	Screening ¹	Brachytherapy	Follow-up ⁶	Follow-up ⁶	Follow-up ⁶	Long term Follow-up ⁶
			1 month +/- 12 weeks	6 months +/- 12 weeks	12 months +/- 12 weeks	24 and 36 months +/- 12 weeks
Informed consent	X					
Medical history	X					
Eligibility criteria	X					
Vital signs	X		X	X	X	
Physical examination	X		X	X	X	
Pelvic exams	X		X	X	X	
WHO/ECOG performance status	X		X	X	X	
QLQ30 Questionnaire²		X	X	X	X	
EN24 Questionnaire²		X	X	X	X	
Collection of Cost Data⁴				X		
Collection of Distance Data⁷					X⁸	
Vaginal Cuff Brachytherapy³		X				
Adverse Event assessments		X	X	X	X	
Chart Review⁵						X
COHORT 2 Only						
COST-FACIT¹⁰			X			
Health Care Expense Survey¹¹		X	X			
NCI Diet History Questionnaire III (DHQ-3)⁹			X			
Physical Activity Questionnaire (ACT24)⁹			X			

1. All Pre-study/Screening procedures should be completed less than or equal to 12 weeks before study treatment.

2. Both the QLQ30 and EN24 questionnaires (appendix E and F) should be administered at baseline (prior to the first brachytherapy fraction) and at the 1 month, 6 month, and 12 month follow-up visits. See section 7.2.1 for guidance on participants experiencing severe emotional distress.
3. Subjects randomized to the control arm will undergo one of the three treatment options described in section 5 over no more than 3 weeks. Subjects randomized to the experimental arm will undergo the treatment described in section 5 over no more than 2 weeks. See Appendix D for treatment planning and dose reporting form.
4. Collection of cost data for analysis is described in section 9.2
5. The PI will continue to review patient medical charts at 24 and 36 months for disease reoccurrence at one of the following locations: vaginal, pelvic, or distant.
6. In person visits are preferred to allow for exams, so almost all visits will be done on site. If a patient is ill or cannot travel, questionnaires and history may be obtained via telemedicine. Missed exams will be considered deviations.
7. Patient's zip code and the location of the treatment facility will be collected and documented by the study staff.
8. If the information is not collected at the 12 month follow up visit, it will be collected at a subsequent time point or from patient's medical record.
9. Completion of the DHQ-3 and ACT24 is strongly encouraged, however, incompleteness will not result in a protocol deviation.

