10.1.6 Sample Size Evaluation

We base the sample size on the precision of estimation of the Global Heath Status from QLQ-C30. The hypothesis to be tested is that the mean Global Health Status will be the same or higher one month after treatment in the Experimental Arm compared to the Control Arm. The EORTC QLQ-C30 reference values manual gives the means and SD of the Global Health Status in genitourinary cancer patients as 62.6 ± 22.2 points. We assume a standard deviation of 22.2 points for power calculations. Additional assumptions are 1:1 randomization to one of two groups, a true difference of 0 points, a Gaussian response variable, a non-inferiority margin of 15 points, alpha = 0.025 (one sided), and the use of a two sample *t*-test for the primary analysis. A non-inferiority margin of 15 points was chosen for this trial based on a combination of scientific and practical considerations. In a survey of 30 clinical trials, the definition of a clinical meaningful change in quality of life questionnaire data varies widely, with margins up to 10-15 point required for clinical significance (Cocks KT, et al 2008). With these assumptions a total evaluable sample size of 96 will provide 90% power. The planned sample size of 108 randomized equally to two arms allows for a dropout rate of approximately 10%.

10.2 COHORT 2

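### The primary non-inferiority test leaves out a baseline score that every analysed patient must have: a valid test, but less precise and open to chance baseline imbalance

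*Combined protocol and SAP*

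**What the plan says.** - **Deciding test.** Section 10.1.1: "A two sample t test will be used for the primary analysis". The Study Summary names the same test, and section 10.1.6 sizes the trial on "the use of a two sample *t*-test for the primary analysis".
- **Analysis set.** Section 10.1.1: "All patients with valid non-missing baseline and one month follow up Global Health Status will be included in the analysis". Section 9.1 also asks for a valid baseline questionnaire.
- **Collection.** Note 2 to the Study Calendar (section 8) says the questionnaires "should be administered at baseline (prior to the first brachytherapy fraction", so the score precedes treatment.
- **Adjusted model.** Section 10.1.1 continues: "As a sensitivity analysis we will use analysis of covariance with Global Health Status at one month post therapy as Gaussian response variable", with arm as a fixed effect and "baseline Global Health Status as a continuous adjustment variable".
- **Randomization.** Section 11 describes a code prepared by a biostatistician and names no stratification factor.
- **Status.** Section 4.2 records that Cohort 1 has been enrolled and analysed. Section 10.2.4 limits Cohort 2 quality-of-life analysis to description, without formal tests.

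The plan gives no reason for ranking the unadjusted test above the adjusted one, and does not say how a disagreement between them would be reported.

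**The concern.** A patient without a baseline score is excluded from the primary analysis, yet the deciding test makes no use of that score. When baseline and one-month scores are correlated, two things follow.

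- **Precision.** The t test leaves in its error term the share of variance that baseline explains. Its confidence interval is therefore wider than that of a model already written for the same patients.
- **Imbalance.** With no stratification described, nothing in the stated design balances baseline quality of life. A chance difference between the arms passes in part into the one-month difference. It can help or hinder the lower confidence limit in clearing -15, whatever the treatments do.

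The second matters more in a non-inferiority trial, because an imbalance favouring the experimental arm makes a wrongly favourable conclusion more likely in that realised sample.

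**Working it through.** **Inputs.** From section 10.1.6: SD 22.2, margin 15, true difference 0, one-sided alpha 0.025, 96 evaluable (48 per arm at 1:1). Assumed, because the documents give neither: the baseline-to-one-month correlation ρ, and a baseline SD equal to 22.2.

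**1. The plan's own figure.**
- SE = 22.2 × √(2/48) = 4.53.
- Noncentrality = 15 / 4.53 = 3.31, with 94 degrees of freedom and critical value 1.986.
- Noncentral t power = 90.6% at 96 evaluable. At 94 it is 89.99%, so 96 is the smallest even total that reaches 90%. The stated figure reproduces.
- 95% CI half-width = 1.986 × 4.53 = 9.0 points. Non-inferiority is therefore declared when the observed difference exceeds about -15 + 9.0 = -6.0.

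**2. The ANCOVA already in section 10.1.1.** Residual SD = 22.2 × √(1 - ρ²), the same SE formula, 93 degrees of freedom:

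| ρ (assumed) | Residual SD | Power at 96 | Gain over t test (points) | 95% half-width |
|---|---|---|---|---|
| 0.1 | 22.1 | 90.9% | +0.3 | 8.9 |
| 0.2 | 21.8 | 91.7% | +1.1 | 8.8 |
| 0.3 | 21.2 | 93.0% | +2.4 | 8.6 |
| 0.5 | 19.2 | 96.6% | +6.0 | 7.8 |
| 0.7 | 15.9 | 99.6% | +9.0 | 6.4 |

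The gain reaches 5 points of power at ρ of about 0.45 (95.6%). At ρ = 0.5 the worst adjusted difference that still passes is about -15 + 7.8 = -7.2, against -6.0 for the t test.

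**3. Chance baseline imbalance.**
- SE of the baseline difference = 22.2 × √(2/48) = 4.53. The probability of a difference of 5 points or more, both directions together, is 2 × [1 - Φ(5/4.53)] = 27%, or about 13.5% each way.
- Given a baseline difference d (experimental minus control), the unadjusted one-month difference has mean (true difference + ρd) and SE 4.53 × √(1 - ρ²). At ρ = 0.5 and d = ±5 the shift is ±2.5 points and the SE is 3.92. The steps below use a normal approximation and the -6.0 threshold.
- True difference -15, d = +5: mean -12.5; (-6.0 + 12.5)/3.92 = 1.66. False non-inferiority rate about 4.9%. With d = 0 it is (-6.0 + 15)/3.92 = 2.29, about 1.1%.
- True difference 0, d = -5: mean -2.5; (-6.0 + 2.5)/3.92 = -0.89. Power about 81%, against about 94% with d = 0.
- For the same 5-point imbalance, ρ of 0.3, 0.5 and 0.7 gives shifts of 1.5, 2.5 and 3.5 points, conditional error of 4.1%, 4.9% and 4.5%, and conditional power of 85%, 81% and 78%. At ρ = 0.1 the conditional error is only about 3.0%.

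Averaged over all possible imbalances, the t test's error rate returns to its nominal 2.5%.

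**The case against.** Much of the case for leaving the plan alone is sound.

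- **The test is valid and consistently planned.** The Study Summary and sections 10.1.1 and 10.1.6 all name it, the sample size was computed for it, and randomization protects its unconditional error rate. This stands. A reader might infer that the primary analysis is invalid or underpowered; step 1 shows it is not.
- **The adjusted analysis is prespecified.** Section 10.1.1 commits to it, and section 10.1.3 adds a repeated-measures model focused on change from baseline. This stands: the baseline score is used, just not in the deciding test.
- **ρ is unknown and could be low.** The scale has two items (Appendix E), the one-month visit has a window of plus or minus 12 weeks (section 8), and chemotherapy may fall before or after brachytherapy (section 6.1.1). At ρ of 0.1 to 0.2 the gain is 0.3 to 1.1 points of power. This stands, and is why the size is given as a range.
- **The movement in the threshold is modest.** At ρ = 0.5 it is 1.2 points on a 0 to 100 scale. That is correct for the change in precision, but it does not answer the imbalance point, where a 5-point difference shifts the estimate by 2.5 points.
- **It is too late to swap.** Given section 4.2, making ANCOVA primary now would change the decision rule after analysis, a worse fault than the one described here. This stands and limits the fix.

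**Conclusion.** The point holds as a design weakness, not an error. The decision rests on the less precise of two analyses specified for the same patients, and the plan gives no reason for that order. The cost ranges from negligible (90.6% against 90.9% power at ρ = 0.1) to substantial (99.6% at ρ = 0.7). At ρ = 0.5 it is 6.0 points of power and 1.2 points of half-width. A chance baseline difference of 5 points or more has about a 27% probability. At exactly 5 points in the experimental arm's favour, the conditional false non-inferiority rate at the margin is about 4.9% at ρ = 0.5.

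These figures rest on the section 10.1.6 inputs, an assumed ρ and an assumed baseline SD of 22.2.

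A reader might go further and infer that the Cohort 1 conclusion is unsafe, or that ANCOVA should now replace it. The documents support neither: they report no observed baseline difference, correlation or result from either model, and the analysis is recorded as complete.

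**What to change.** **As a design choice.** The ANCOVA in section 10.1.1 should have been primary, with the lower limit of the two-sided 95% CI for the adjusted arm difference compared with -15 and the t test kept as the sensitivity analysis. Section 10.1.6 would then name ANCOVA.

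**What can be done now, given section 4.2.**
1. Keep the t test as the prespecified decision for Cohort 1.
2. In every report of the primary result, give the prespecified ANCOVA difference and its 95% CI against -15 beside the t test, and state whether the two agree.
3. Use the baseline-adjusted model for any later between-arm estimate of Global Health Status. Section 10.2.4 plans no such test in Cohort 2, so this applies only if one is added.

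**Cost.** Reporting text only. Both scores are already required and the model is already written, so no new patients, data or decision rule are needed. The ANCOVA must stay labelled as the planned sensitivity analysis, so that its added prominence is not read as a changed primary analysis.

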10.1.2 Handling of missing items in the Global Health Status

If at least half the items in the Global Health Status are present then the Global Health Raw Score will be calculated as the average of the items that are present. This method is effectively equivalent to replacing missing items by the average of the items that are present, and is a standard method for treating summary scores with missing items. If more than half the items are missing the Global Health Status will be treated as missing. Subjects with missing Global Health Status will be excluded from the primary analysis. This method provides valid estimates provided data is missing at random (MAR). Sensitivity analyses may be performed with multiple imputation used to impute missing data.

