9 CRITERIA FOR EVALUATION AND ENDPOINT (COHORT 1)

9.1 Primary Objective

Evaluate the non-inferiority of patient HRQOL using the Global Health Status from the QLQ-C30 in the 2 arms one month after treatment.

All patients with a valid baseline and with a follow-up QOL questionnaire at one month post treatment will be included in the analysis. We are accounting for an approximate 5 per cent drop out rate. We anticipate a high compliance rate due to the short follow up interval for the primary endpoint. Patients without valid questionnaires will not be replaced. The baseline questionnaire is considered valid if filled out and dated by the patient before the starting date of trial treatment. Reasons for missing baseline and follow-up questionnaires will be assessed.

For the evaluation of the general quality of life the EORTC (European Organization for Research and Treatment of Cancer) Core questionnaire (QLQ-C30 version 3.0) will be used (Appendix E). The EORTC QLQ-C30 is a multidimensional, cancer-specific quality of life questionnaire developed by the EORTC Study Group on Quality of Life (QOL) for repeated assessments within clinical trials. It is developed in a cross- cultural setting and has been found valid and reliable for quality of life assessments in various cancer populations, irrespective of the specific diagnosis. Optional modules developed for specific diagnostic groups or specific treatment modalities can supplement it. The QLQ-C30 contains five functional scales (physical, cognitive, emotional, social and role functioning), a global health status/quality of life scale, three symptom scales (pain, fatigue and nausea/vomiting), and six single items assessing additional symptoms (dyspnoea, insomnia, loss of appetite, constipation, diarrhoea) and perceived financial impact. For the majority of the QLQ-C30 items a 4-point Likert-type response scale is used. Exceptions are the items for the global quality of life scale (where a 7-point scale is used). All subscale and individual item responses are linearly converted to 0 to 100 scales. A higher score for a functional and global quality of life scales represents a better level of functioning. For the symptom scales and items, a higher score reflects a higher level of symptoms and decreased quality of life.

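### Section 10.1.2 calls the complete-case analysis valid under MAR, but MAR given baseline is not enough for an unadjusted t test; the wording needs correcting, though material bias is not shown

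*Combined protocol and SAP*

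**What the plan says.** All references are to the combined protocol and SAP.

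- **Analysis set (Section 10.1.1):** "All patients with valid non-missing baseline and one month follow up Global Health Status will be included in the analysis". Section 9.1 gives a matching rule.
- **Primary test (Section 10.1.1):** "A two sample t test will be used for the primary analysis". It uses the one-month score only.
- **Baseline adjustment (Section 10.1.1):** baseline enters through a firm but secondary analysis: "As a sensitivity analysis we will use analysis of covariance with Global Health Status at one month post therapy as Gaussian response variable", with "treatment group as a fixed effect and baseline Global Health Status as a continuous adjustment variable".
- **Missing scores (Section 10.1.2):** "Subjects with missing Global Health Status will be excluded from the primary analysis". The next sentence is "This method provides valid estimates provided data is missing at random (MAR". Imputation is optional: "Sensitivity analyses may be performed with multiple imputation used to impute missing data".
- **Repeated measures (Section 10.1.3):** an exploratory normal model with unstructured covariance covers baseline, 1, 6 and 12 months. It too excludes subjects with a missing score.
- **Expected loss:** about 5% in Section 9.1 and about 10% in Section 10.1.6.
- **Status (Section 4.2):** enrolment and analysis of Cohort 1 are complete.

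**The concern.** MAR means that missingness may depend on observed data, and here the observed data include the baseline score. A method that conditions on baseline can exploit that; an unadjusted comparison of one-month means cannot. Suppose patients with poor baseline scores fail to return the one-month form more often in one arm. The remaining patients in that arm are then a favourable selection, and the t test reads part of that selection as a treatment effect.

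In a non-inferiority trial the direction matters. Losing low scorers mainly from the experimental arm favours a non-inferiority claim, while losing them mainly from control makes the test conservative. The plan's sentence tells a reader that the estimate can be trusted under a condition that does not rule out either case.

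Section 10.1.3 has a related flaw. A likelihood-based repeated-measures model can use patients with some scores missing, so excluding them discards information for no gain.

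**Working it through.** **1. The plan's own figure.** Inputs from Section 10.1.6: margin 15, SD 22.2, true difference 0, one-sided alpha 0.025, t test. With 48 per arm, SE = 22.2 × sqrt(2/48) = 4.53. The noncentral t gives power 0.906, and 0.8999 at 47 per arm, so 96 evaluable for 90% reproduces. 96/0.9 = 106.7, or 107, against 108 planned. The sample size is not in question.

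**2. Bias when missingness depends on baseline in one arm only.** Assumptions, since the documents give neither quantity: baseline to one-month correlation r = 0.3 to 0.7, and logit of missingness linear in standardised baseline with slope -0.5 to -1.5. The 5% and 10% losses come from Sections 9.1 and 10.1.6 and apply to both arms; only one arm's loss depends on baseline.

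Bias = 22.2 × r × m, where m is the mean standardised baseline among patients still observed in the affected arm.

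| Slope | m at 5% / 10% | Bias at 5%, r 0.3 to 0.7 | Bias at 10%, r 0.3 to 0.7 |
|---|---|---|---|
| -0.5 | 0.0247 / 0.0488 | 0.16 to 0.38 | 0.33 to 0.76 |
| -1.0 | 0.0471 / 0.0908 | 0.31 to 0.73 | 0.60 to 1.41 |
| -1.5 | 0.0648 / 0.1217 | 0.43 to 1.01 | 0.81 to 1.89 |

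Example: 22.2 × 0.7 × 0.1217 = 1.89. The steep end is severe: at slope -1.5 and 10% missing, 51% of patients 2 SD below the baseline mean are lost, against 0.3% of those 2 SD above. At slope -0.5 these are 21.5% and 3.6%.

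**3. One-sided error at a true difference of -15.** Error = 1 − Φ(1.96 − bias/SE), SE = 22.2 × sqrt(2/n), n = 54 × (1 − missing). SE is 4.38 at 5% and 4.50 at 10%.

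- Experimental arm affected: 2.7-3.7% at slope -0.5, 3.0-5.0% at -1.0, 3.1-6.2% at -1.5, against 2.5% nominal.
- Control arm affected: same sizes with the sign reversed; error 0.9-2.3%.
- Same selection and same baseline to one-month relation in both arms: the two shifts cancel and bias is 0.

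Simulation of 40,000 trials of 54 per arm agreed for the experimental-arm case: t-test error 2.7-3.6% at slope -0.5 and 3.2-6.1% at -1.5. ANCOVA on the same patients had bias 0.01-0.02 points and error 2.5-2.6%.

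**4. Power at a true difference of 0, 48 per arm.** From 90.6%, it becomes 93.1% or 87.5% at a bias of +0.76 or -0.76, and 95.8% or 81.7% at +1.89 or -1.89.

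**5. Section 10.1.3 taken literally.** Assume 5% or 10% missing independently at each of three follow-ups and complete baselines. Patients kept per arm: 54 × 0.95³ = 46.3 or 54 × 0.90³ = 39.4. Those with a one-month score: 54 × 0.95 = 51.3 or 54 × 0.90 = 48.6.

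**The case against.** The sentence names no conditioning set. If MAR is read as missingness depending on arm alone, it is correct for the t test. It might also be meant for the half-item scoring rule earlier in the section. Both readings are possible, but the sentence directly follows the exclusion rule, and the ordinary meaning of MAR includes observed baseline. The plan would have to state the narrower meaning for the sentence to hold.

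The plan has real safeguards: a firm ANCOVA, assessment of reasons for missing forms (Section 9.1) and telemedicine questionnaires for patients who cannot travel (Section 8, footnote 6). Cohort 1 is also already analysed, and Cohort 2 does not use this test. These arguments stand. They limit the point to wording and reporting.

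Three stronger inferences are tempting, and the documents do not support them.

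- **The primary result is biased.** No missingness by arm, slope or correlation is given, and the bias is zero when the mechanism and the baseline relation are shared.
- **The ANCOVA fails as well.** With identical selection but r = 0.7 in one arm and 0.3 in the other, both analyses are biased by about 0.2 to 1.1 points (22.2 × 0.4 × m). Nothing in the documents suggests such a contrast. A mild quadratic baseline relation (assumed) gives ANCOVA bias of only about 0.2 to 0.3 points. This is a reason to state its conditions.
- **Requiring a baseline costs power.** Those losses already fall within the planned reduction from 108 to 96.

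**Conclusion.** The point holds as a correction of a stated property. MAR, as usually understood, does not make the complete-case t test valid. Under the assumptions above, the bias runs from about 0.2 to 1.9 points in either direction, or 1% to 13% of the 15-point margin (0.16/15 to 1.89/15). One-sided error reaches about 6% at the extreme when the bias favours the experimental arm. That inflation is relevant only if the true difference is close to -15.

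Material bias is not shown, and the primary analysis need not change. The ANCOVA already planned deals with this mechanism when missingness depends only on arm and baseline and the baseline relation is linear with a common slope. The exclusion rule in Section 10.1.3 affects an exploratory analysis only, but it loses data needlessly.

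**What to change.** 1. Replace the MAR sentence in Section 10.1.2 with: *The complete-case t test is valid if, within each arm, missingness is unrelated to the one-month score, or if it depends on baseline in the same way in both arms with the same baseline to one-month relation. The ANCOVA is valid if missingness depends only on arm and baseline and the baseline relation is linear with a common slope.*
2. Keep the t test as the primary result. Report the pre-specified ANCOVA beside it, with missing counts and reasons by arm, and state whether the two agree on non-inferiority.
3. Delete the exclusion sentence in Section 10.1.3 and fit the repeated-measures model to all available scores.

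Since Cohort 1 has been analysed, label any re-run as post hoc. The cost is a few sentences and re-runs on existing data, with no extra patients or visits.

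A separate minor point, unrelated to MAR: Section 9.1 counts a baseline form as valid only if dated before the day treatment starts, while footnote 2 of Section 8 asks for it before the first fraction. The two must be reconciled.
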